9.4 Correlative Biology Studies

9.4.1 Study design for Study Objective 1.2.1 (FLT3 Mutations)

A Fisher's exact test will be used to compare the Induction death rate for patients with FLT3 mutations to patients with wild type FLT3. Assuming 140 patients have FLT3 results available and a FLT3 mutation prevalence of 40% (based on prior pediatric APL data), this study will have 80% power with two-sided 0.05 type I error to detect differences of 19.5% and 15.5% in Induction death rates for Induction death rates of 30% and 20%, respectively, for FLT3 mutant patients.⁴² The mutational analysis will be performed on diagnostic samples with an expected sample size of 140 and average accrual of 2.3 patients/month.

9.4.2 Study design for Study Objective 1.2.2 (Bone Marrow and Peripheral Blood MRD Testing)

For patients in remission at the end of Induction, the log-rank test will be used to test for differences in disease free survival (DFS) for those with end of Induction RQ-PCR of < 1 normalized copy number (NCN) compared with those with end of Induction RQ-PCR ≥ 1 NCN. Assuming 90% of patients are in remission at the end of Induction and 65% of these have specimens available to be analyzed by PCR, there will be at least 85 patients in remission at the end of Induction with PCR results. This corresponds to an average accrual rate of 1.4 patients/month. This study will have 80% power with two-sided 0.05 type I error to detect a difference of 32% in 5-year DFS (90% vs. 58%, 5.2 hazard ratio).

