2.6 Risk Stratification Based on WBC

The risk criteria first published by Miguel Sanz based on WBC and platelet counts have proven to be predictive in pediatric patients.⁶ Standard risk disease (including both low and intermediate risk groups by Sanz criteria) includes patients with an initial WBC < 10,000 at diagnosis. High risk disease includes patients with WBC \geq 10,000. On the AIDA 0493 study, pediatric patients with high risk disease had a worse EFS compared to those with standard risk disease. Early Induction deaths due to differentiation syndrome and coagulopathy occur more frequently in patients with high risk disease. The risk of relapse is also higher in patients with high risk disease. In this trial, therapy for high risk APL will differ from standard risk APL in that it will include 4 doses of idarubicin early in Induction. The goal of idarubicin for patients with high risk disease is to decrease risk of relapse as well as to decrease the white blood cell count (due to the associated early complications seen with uncontrolled leukocytosis).

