9.0 STATISTICAL CONSIDERATIONS

9.1 Statistical Design

This is a non-randomized study of pediatric patients with APL stratified by risk group based on presenting WBC. Patients with standard risk disease (WBC < 10,000/ μ L at diagnosis) and high risk disease (WBC \geq 10,000/ μ L at diagnosis) will be assessed independently for outcome measures. The primary endpoint will be event-free survival (EFS). EFS is defined as the time from on study to failure to achieve hematological CR prior to start of Consolidation, persistence of molecular positive disease after MRD Positive Consolidation course (mitoxantrone/cytarabine/ATRA chemotherapy course following Consolidation Cycle 2), relapse (molecular, morphologic or extramedullary), or death.

Other outcome measures will include the hematological, molecular, and cytogenetic remission rates after each phase of therapy, early death rates, overall survival from on study, treatment related mortality, relapse risk, percentage of patients experiencing Grade 3 or higher toxicity or any grade of cardiac toxicity, time to count recovery, and duration of hospitalization.

When AAML1331 was developed and opened, outcome data from the most recent prior COG APL study AAML0631 was not mature. Thus, similar to AAML0631, the statistical plan of AAML1331 initially used the historical comparator AIDA 0493 (the most mature and best outcomes published for pediatric APL). During the course of AAML1331 accrual, AAML0631 outcome data became available and demonstrated that the addition of arsenic trioxide (ATO) consolidation therapy resulted in higher survival estimates compared to AIDA0493. Therefore the statistical plan of AAML1331 was amended to include a primary outcome comparison to AAML0631.

AAML0631 included 2 cycles of ATO consolidation and has excellent survival results. Thus, we would not expect AAML1331 to be significantly superior to AAML0631, but rather the goal of the study should be to show non-inferiority to AAML0631. This design is clinically appropriate because the AAML1331 treatment regimen represents a significant reduction in cytotoxic chemotherapy treatments which should result in decreased toxicities (both in the short and long term). To demonstrate that AAML1331 therapy is non-inferior to AAML0631 would be a major step forward in reducing treatment morbidity and mortality.

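### The FLT3 and MRD tests pool standard- and high-risk patients without stratification, so they would be biased if marker status differs by risk group and cannot show that a marker adds to WBC risk group

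*Combined protocol and SAP*

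**What the plan says.** Section 9.4.1 plans an "exact test will be used to compare the Induction death rate for patients with FLT3 mutations to patients with wild type FLT3". It assumes 140 patients with results and 40% mutant, and claims "80% power with two-sided 0.05 type I error to detect differences of 19.5% and 15.5% in Induction death rates" for mutant death rates of 30% and 20%.

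Section 9.4.2 takes patients in remission after Induction and states that "the log-rank test will be used to test for differences in disease free survival (DFS") between end-Induction NCN below 1 and NCN of 1 or more. It expects that "there will be at least 85 patients in remission at the end of Induction with PCR results" and claims 80% power to "detect a difference of 32% in 5-year DFS (90% vs. 58%, 5.2 hazard ratio").

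Neither section names a stratification factor, a covariate or an analysis by risk group. Yet Section 9.1 says of the two risk groups that they "will be assessed independently for outcome measures", and it counts early death and relapse risk among the other outcome measures. Section 2.6 says: "Early Induction deaths due to differentiation syndrome and coagulopathy occur more frequently in patients with high risk disease". It adds that relapse is also more frequent in high-risk disease and that only high-risk patients receive idarubicin in Induction. Section 2.10.1 plans to correlate FLT3 status with presenting WBC, the variable that defines the risk groups, but describes no adjustment.

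**The concern.** Risk group is tied to both outcomes being tested. For MRD it is also tied to treatment given before the marker is read: high-risk patients receive idarubicin and prophylactic dexamethasone before the Day 29 sample. If the marker is also tied to risk group, the pooled comparison partly compares high-risk with standard-risk patients, and a marker that only tracks WBC could be declared prognostic.

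The protocol names uses for these results: future FLT3-inhibitor trials (Section 2.10.1), and reduced treatment and monitoring for patients with low NCN (Section 2.10.2). WBC already determines treatment, so both uses need to know what the marker adds to it. A pooled test cannot say.

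**Working it through.** **1. Are the designs really pooled?** Section 9.2 plans 96 SR and 54 HR patients, 150 in all. The 140 in 9.4.1 exceeds either group. For 9.4.2, 150 × 0.90 × 0.65 = 87.75, which matches its figure of at least 85. For FLT3, 40% of 140 gives 56 mutant and 84 wild type. Exact enumeration of Fisher's test at two-sided 0.05 gives:

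- 30% vs 10.5%: power 80.0%
- 20% vs 4.5%: power 79.7%

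The plan's 80% is therefore reproduced by a pooled, unstratified test.

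**2. How bias would arise (FLT3).** Splitting 140 in the ratio 96:54 gives about 90 SR and 50 HR. The documents give neither FLT3 prevalence nor Induction death by risk group, so all values below are assumptions. Both unequal prevalence pairs keep 40% overall:

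- 30%/58%: 27 + 29 = 56 mutants
- 25%/67%: 22.5 + 33.5 = 56 mutants

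Take 25%/67%, Induction death 2% SR and 10% HR, and no marker effect within either group:

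- mutant: (22.5 × 0.02 + 33.5 × 0.10)/56 = 3.80/56 = 6.8%
- wild type: (67.5 × 0.02 + 16.5 × 0.10)/84 = 3.00/84 = 3.6%

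The spurious difference is 3.2 points, an odds ratio of about 1.97.

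**3. Type I error of the pooled Fisher test** (simulated, no true effect, two-sided 0.05; repeat runs agree to about 1 point):

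| Induction death SR/HR | Overall death (0.64 × SR + 0.36 × HR) | Prevalence 30%/58% | Prevalence 25%/67% |
|---|---|---|---|
| 0.5%/4% | 1.8% | 2% | 3% |
| 2%/8% | 4.2% | 5% | 7% |
| 2%/10% | 4.9% | 6% | 10% |
| 3%/15% to 5%/20% | 7.3% to 10.4% | about 9% | 14-17% |

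With 40% prevalence in both groups the pooled test stays at about 1-3.5%. The exact stratified test is at most about 4% throughout. Cochran-Mantel-Haenszel (CMH) by risk group runs at 4.2-5.5% for death of 2%/10% to 5%/20%.

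**4. Which rows are plausible?** Section 2.10.3 reports four early deaths in AAML0631 among the 76 patients with complete coagulation data, out of 102. That is 4/76 = 5.3% or 4/102 = 3.9%, close to the 2%/8% and 2%/10% rows. The Section 9.3.3 cure models point the same way or lower:

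- SR failure at 24 months: 1 − [0.906 + 0.094 exp(−0.0238 × 24)] = 4.1%
- HR failure at 24 months: 1 − [0.7973 + 0.2027 exp(−0.0976 × 24)] = 18.3%
- By Days 28-70: 0.2-0.5% SR and 1.7-4.1% HR, all causes

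Induction death of 5%/20% would exceed all two-year failure in both groups.

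**5. MRD.** With 85 patients, 36% HR and no marker effect, the pooled log-rank test rejects in 4-5% of runs if the share with NCN of 1 or more is equal (66%/66%). It rejects in 4-16% if the share is 55%/85% to 50%/95%, with assumed five-year DFS (SR/HR) of 96%/85%, 91%/71% or 83%/59%. The stratified log-rank gives 4-6%. The last two pairs match EFS figures that Section 2.1 gives for AIDA 0493, so they overstate the contrast for a DFS test in patients already in remission. Section 2.3 reports similar five-year relapse on APML4, whose idarubicin Induction is the model for high-risk patients here: 4.5% SR and 5.3% HR. At those rates the pooled test rejects in about 3% of runs, even with NCN shares of 45%/95%.

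**The case against.** A reader might infer that the marker effects are confounded with risk group. The documents do not support that. Confounding needs marker status to differ by risk group, and no section gives FLT3 prevalence or NCN by risk group. Section 2.10.1 only plans to look at FLT3 against WBC. With equal prevalence the pooled test keeps its level. This stands, and the point is therefore conditional.

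A reader might also take the top of the range as the expected inflation. Those death rates sit badly with the AAML0631 figures in step 4. Against that, 9.4.1 itself powers on 20-30% death in mutants, which implies 0.4 × 20% + 0.6 × 4.5% = 10.7% overall or more. That is a design alternative, not an observed rate, so the top row is the unfavourable end.

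For MRD the documents point both ways on relapse: Section 2.6 says it is higher in high-risk disease, while Section 2.3 reports similar rates on APML4. No firm size can be given.

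Sections 2.10.1 and 2.10.2 ask whether the markers are prognostic, not whether they are independently so. If FLT3 mutation acts by raising WBC (an assumption), stratifying removes that part of its effect. This argues for keeping the pooled result, not for leaving the stratified one out.

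Finally, the aims are exploratory, Section 15.0 says the results guide no treatment, and the primary EFS analyses are already separate by risk group. This limits the consequence but does not answer the point, because the protocol names later uses that depend on the added value of the marker.

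**Conclusion.** The point holds in conditional form. Both tests are pooled and unstratified, which is at odds with the general statement in Section 9.1 and ignores differences described in Section 2.6. If marker status differs by risk group, the tests are biased. Whether or not it differs, they cannot show that a marker adds to WBC risk group.

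For FLT3, under the assumed prevalence imbalances, type I error is about 2-3% at the lowest death rates and 5-10% at rates near the AAML0631 early-death figure. It reaches 9-17% only at the unfavourable end. For MRD the inflation is uncertain and may be nil. This is a change worth making to exploratory analyses; it does not touch the primary objectives.

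**What to change.** In Section 9.4.1, specify a CMH test or an exact conditional test stratified by risk group. In Section 9.4.2, specify a log-rank test stratified by risk group. Report estimates for each risk group, keep the pooled Fisher and log-rank tests as the unadjusted result, and say how this fits with the statement in Section 9.1.

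No new data are needed, because the initial CBC defines risk group for every patient (Section 3.3).

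- **FLT3 power.** At common odds ratios of 3.65 and 5.31 (the plan's two effects), with HR odds of death assumed four times SR odds, CMH power is 78-80%. The power statement should be restated for the stratified test. The exact test is more conservative than CMH.
- **MRD power.** Section 9.4.2 gives no NCN split or event count, so no target can be carried over. With a hazard ratio of 5.2 and equal NCN shares (66%), simulated power is 90% pooled and 90% stratified. With shares of 55%/85% and assumed low-NCN DFS of 94%/83%, stratified power is 77%.
- **Interpretation.** If FLT3 acts through WBC, the stratified result leaves that part out, so the pooled result should be shown beside it.

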9.4.3 Study design for Study Objective 1.2.3 (Early Death and Coagulopathy Complications)

Adverse event reporting will be used to estimate the rate of serious early coagulopathy events (Grade 3 or higher hemorrhage or thrombosis from diagnosis through end of Induction). We will calculate the ISTH DIC score as has been previously described⁴⁹ and compare the sensitivity and specificity (to accurately predict patients who will experience a serious early coagulopathy event) of ISTH with that of thrombomodulin using McNemar's test for paired data. Based on a

target accrual of 150 patients for AAML1331, if all patients participate in this biology study with submission of specimens and the clinical data required to calculate ITSH, then the average accrual rate will be 2.5 patients/month. Estimating that serious early coagulopathy events occur in 20% of the patients (based on the rate seen in AAML0631), then there will be 30 AAML1331 patients with these events. AAML1331 will have 81% power to detect a difference in sensitivities of 22% (68% vs. 90%) using a 1 sided test with 0.05 significance level assuming 23% proportion discordant. There will also be at least 90% power to detect a difference in specificities of 20% (66% vs. 86%) using a 1 sided test with 0.05 significance level. To improve the predictive ability of the ISTH DIC score, we will use a stepwise combination of biomarkers (elevation in thrombomodulin levels, thrombin generation, fibrinolytic parameters and microparticles). Receiver operating characteristic (ROC) curve will be used to assess the accuracy in prediction of bleeding events during Induction and the areas under the ROC curve (AUC) will be compared.

9.4.4 Study design for Study Objective 1.2.4 (Neurocognitive Outcomes)

The primary objective of this study is to use CogState testing to evaluate change in neurocognitive function from end of Induction to 2 years off therapy. The three secondary objectives include first, use of parent-reporting on the BRIEF questionnaire to assess change in neurocognitive function from end of Induction to 2 years off therapy, and for the other secondary aims, use of a psychologist administered battery to assess change in neurocognitive function from end of therapy to 4 years off therapy.

Actual CogState scores for each domain at each time point will be summarized and examined by descriptive statistics and scatter plots. Change in score for a domain from end of Induction will be calculated and similarly summarized by descriptive statistics. For the CogState scores, the mean change of score from end of Induction to a later time point will be estimated along with its 95% CI. One sample t-test on the change of score will be used to examine if there is significant decline in neurocognitive function from end of Induction to 2 years off therapy. Thus our analysis of CogState outcome data will be restricted to participants who have completed CogState testing following Induction (i.e., we will include data from patients who are 5 years of age or older by Day 1 of Consolidation Cycle 1). Outcomes for younger patients not completing the initial Induction assessment will be reported in a descriptive manner. Linear mixed models using scores from all time points as outcome will also be used to estimate the change in scores between time points with adjustment for within-patient correlation of the score by random effects for individual patients. If the change in score over time appears approximately linear in time, linear mixed models assuming time as a continuous covariate will be used to estimate the rate of decline over time and determine whether the rate of decline is significantly higher than zero.

Since each domain will be analyzed separately, the alpha level for each analysis is set to 0.01 for CogState and the psychologist administered battery and 0.017 for BRIEF according to Bonferroni adjustment to maintain an overall alpha of 0.05. For the primary objective utilizing CogState testing, assuming that there are 120 patients 5 - 18 years old who consent to participate in neurocognitive testing and receive all protocol therapy, there will be 80% power to detect the unit change

provided in the table below in the mean change score between end of Induction and 2 years off therapy using a one-sample t-test at two-sided alpha level for the SD of the change of score between two time points provided in the table below. For the secondary objectives, mean change score will be compared from end of Induction to 2 years off therapy for the BRIEF and from end of therapy to 4 years off therapy for the psychologist administered battery, BASC-2 Anxiety, Depression, and Social Skills scores, and the PedsQL Total and Physical Health scores.

Outcome	Unit Change	Change SD
CogState (each of five tasks)	4.3	13.6
BRIEF (each of three tasks)	4.3	14.5
Estimated IQ	6.7	20.4
CVLT Total Score	4.3	13.6
Processing Speed Index	6.5	20.4
CMS Stories and Faces Immediate Memory	1.3	4.1
ABAS-II General Adaptive Composite	6.5	20.4
BASC-2 (each of three scales)	8.2	26.0
PedsQL (each of two scales)	10.3	32.4

In AAML0631, 91.7% of participants were between the ages of 5 and 18 and the upper age of enrollment was 21 years of age. Therefore, we would anticipate 91.7% or 138 of the 150 subjects in the proposed sample to be 5 - 18 years old. Based on the accrual to date to this optional embedded study, we project that up to 120 patients 5 - 18 years old will participate in neurocognitive testing and receive all protocol therapy.

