Arsenic Trioxide (ATO): IV daily over 2 hours (may lengthen infusion to 4 hours if active vasomotor symptoms occur)

Days: 1 - 28 minimum. Continue beyond Day 28 if not in hCR/hCRi up to a maximum of 70 days (See [Section 10.2](#) for response criteria and definition of hCR/hCRi).

Dose: 0.15 mg/kg/day (no maximum dose)

Indications for intrathecal therapy

CNS Bleed

Patients with documented CNS bleed will receive CNS prophylaxis to include triple intrathecal chemotherapy at Day 29 of Induction. See table below for age-based dosing.

CNS Disease

Patients with CNS disease (see [Section 3.3.4](#) for definition) will receive twice weekly triple intrathecal chemotherapy (with a minimum interval of 48 hours between treatments) until the CSF is cleared plus two additional twice weekly treatments (minimum of 4 and maximum of 6 treatments). During Induction, patients with CNS disease will also receive a 10 mg/m² dose of leucovorin, 24 hours after each of the twice weekly intrathecal therapies.

Age-based dosing of triple intrathecal therapy:

Age	Triple Intrathecal Therapy (ITT)		
	Methotrexate	Hydrocortisone	Cytarabine
1 - 1.99 years	8 mg	15 mg	30 mg
2 - 2.99 years	10 mg	25 mg	50 mg
≥ 3years	12 mg	35 mg	70 mg

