4.3.3 Consolidation Cycle 1 Treatment Details – Standard Risk APL

Consolidation Cycle 1 lasts 56 days.

Tretinoin (ATRA): PO divided BID

Days: 1 - 14 and 29 - 42

Dose: 12.5 mg/m²/dose, twice daily. The total dose is 25 mg/m²/day divided twice daily.

Administer with food. Refer to [Appendix II](#) for dosing table (includes dose recommendations for very young patients).

Arsenic Trioxide (ATO): IV over 2 hours (may lengthen infusion to 4 hours if active vasomotor symptoms occur)

Days: 1 - 5, 8 - 12, 15 - 19 and 22 - 26

Dose: 0.15 mg/kg/day (no maximum dose)

NOTE: Some patients may require infusion in a clinic setting (i.e. unable to arrange home infusion) and holidays may result in intermittent clinic closure. Therefore it is permissible for patients to miss doses of ATO on those days at the discretion of the treating physician. It is suggested that patients not miss more than 2 doses in a 4 week period (10% of doses). If more than 2 doses are missed in a 4 week period due to holidays, then make-up doses (following Day 26) may be administered at the discretion of the treating physician.

Indications for intrathecal therapy

Intrathecal Triple Therapy (ITT): Only for patients with documented history of CNS bleed or CNS positive disease.

Days: 15 and 43

Dose: Age based dosing as follows:

Age	Triple Intrathecal Therapy (ITT)		
	Methotrexate	Hydrocortisone	Cytarabine
1 - 1.99 years	8 mg	15 mg	30 mg
2 - 2.99 years	10 mg	25 mg	50 mg
≥ 3 years	12 mg	35 mg	70 mg

Proceed to Consolidation Cycle 2 on Day 57 or when blood counts recover (ANC ≥ 1,000/μL and platelet count ≥ 100,000/μL), whichever occurs later. See [Section 4.4](#) for details.

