16.4.1 Schedule of Observations

In previous literature describing neurocognitive effects in both pediatric cancer populations and in children who have been exposed to heavy metals, some changes may appear acutely (and later resolve), whereas other cognitive changes may take years to fully emerge. The assessment intervals are designed to be able to detect both acute neurocognitive changes as well as more subtle changes that would emerge over time, according to the schedule listed below.

Observation Number	Treatment Phase	CogState battery	BRIEF	Psychologist battery
1	Day 1 of Consolidation Cycle 1 (+/- 2 weeks)	✓	✓	
2	Day 1 of Consolidation Cycle 3 (+/- 2 weeks)	✓	✓	
3	End of therapy (+ 3 months)	✓	✓	✓
4	2 years Off-therapy (+/- 3 months)	✓	✓	✓
5	4 years Off-therapy (+/- 3 months)	✓	✓	✓

It is important to note that the CogState battery has not been validated in children less than 5 years of age, which means that we will be unable to capture data from computerized testing from children who are less than 5 year at diagnosis. In AAML0631, only 6 eligible participants (5%) were enrolled who were less than 5 years, so it is likely that we will have similarly few children enrolled on this trial in this age range. However, in an effort to capture information about cognitive changes in this vulnerable age group, we will attempt to collect computerized neurocognitive data (i.e., CogState) for children who are under age 5 at enrollment as soon as they turn 5 years of age. In addition, we will collect data from the performance-based measures for patients once they turn 30 months of age. Of note, the psychologist administered battery also includes standardized measurement of adaptive functioning, including developmental milestones for young patients, which may be particularly relevant in describing outcomes of interest for this age group.

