16.6 Feedback to Participants

Real-time scoring is available for the CogState measure; thus, scores for each participant may be generated immediately. CogState is not designed to be a comprehensive measure

of neurocognitive functioning; however, problems identified by CogState may indicate that the patient may require a more complete neuropsychological evaluation. Consistent with the existing protocol developed for AALL1131, we plan to inform the health care providers of participants who have scored in the bottom 7% (i.e., 1.5 SD below the mean) relative to the standardization sample for CogState, or in the most extreme 7% of scores on the BRIEF, given that extreme scores on either of these measures may reflect significant difficulties that can interfere with learning. Score reports for the BRIEF and CogState are generated automatically by the scoring programs for each measure. When children receive scores at or more extreme than 1.5 SD from the mean, their health care team will be informed of the results in the form of a letter listing the scores of concern, provided by the correlative study research team. There will not be recommendations for dose modification based on the CogState score alone, as this battery has not been validated in this manner. The health care team can follow up with families to determine if further assessment is warranted based on whether or not families are observing difficulties in their child's functioning at home or in school, and make a referral as they would normally do when families report concerns of this kind.

With regard to the psychologist administered battery, the first administration of traditional tests will be at the end of therapy and thus results will not impact individual patient treatment decisions or dose modification.

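### Neurocognitive change is tested from post-arsenic baselines with no group comparison against norms: this hides all on-treatment deficits in the psychologist battery, and those acquired by the first visit in CogState and BRIEF

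*Combined protocol and SAP*

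**What the plan says.** Section 2.10.4 gives the purpose as following the cognitive side effects of this treatment over time, and stresses the effect of arsenic on the developing brain. Section 16.4.1 says the visit schedule should catch both early and late effects, because "some changes may appear acutely (and later resolve), whereas other cognitive changes may take years to fully emerge".

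The first CogState and BRIEF assessment is at "Day 1 of Consolidation Cycle 1 (+/- 2 weeks" (Section 16.4.1). Later ones are at Consolidation Cycle 3 Day 1, end of therapy, and 2 and 4 years off therapy. For the psychologist battery, "the first administration of traditional tests will be at the end of therapy" (Section 16.6). No neurocognitive test is scheduled before ATO.

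The primary CogState analysis in Section 9.4.4 is to "evaluate change in neurocognitive function from end of Induction to 2 years off therapy", by a one-sample t-test on the change score. BRIEF uses the same interval. The other contrast runs "from end of therapy to 4 years off therapy for the psychologist administered battery". Mixed models use all time points and, if the trend looks linear, test the rate of decline against zero. For levels as opposed to changes, "Actual CogState scores for each domain at each time point will be summarized and examined by descriptive statistics and scatter plots". Norms are used only in Section 16.6, to flag individual patients to their care team.

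**The concern.** A change score shows only what happens after its baseline. If arsenic or the rest of treatment has already lowered performance by then, the loss sits in the reference value. A lasting loss produces no change, and a temporary one produces apparent improvement as it resolves. Without a pre-treatment test, a control group or a normative reference for the group mean, nothing else in the planned inference would reveal it.

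The error runs towards reassurance. A regimen that lowers scores on treatment could be reported as showing no decline in IQ, memory, verbal learning, processing speed or adaptive function, although Section 16.1 lists these contrasts among the endpoints that define the treatment's cognitive side effects.

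**Working it through.** **Inputs**
- ATO in Induction: "1 - 28 minimum. Continue beyond Day 28 if not in hCR/hCRi up to a maximum of 70 days", daily (Section 4.2.3; Section 4.8.3 has the same range for high risk). That is 28 to 70 scheduled doses.
- ATO per Consolidation cycle: "Days: 1 - 5, 8 - 12, 15 - 19 and 22 - 26" (Section 4.3.3), so 4 × 5 = 20 doses. Four cycles give 80.
- Section 9.4.4: n = 120, two-sided alpha 0.01 for CogState and the battery, 0.017 for BRIEF. Detectable change and SD of change: CogState 4.3 and 13.6, BRIEF 4.3 and 14.5, estimated IQ 6.7 and 20.4, Processing Speed 6.5 and 20.4.
- Section 16.1: a CogState decline is defined as 5 units.

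**Reproducing the plan's power.** One-sample t-test, df = 119, noncentrality = (change / SD) × √120. For CogState, 4.3 / 13.6 × 10.95 = 3.46, giving 79.9% power. BRIEF gives 79.5%, Processing Speed 80.7% and estimated IQ 83.4%. The stated 80% is sound. The issue is what the change score estimates.

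**Share of scheduled ATO given before each baseline**

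| Baseline | 28-day Induction | 70-day Induction |
|---|---|---|
| CogState/BRIEF, Cycle 1 Day 1 | 28/108 = 26% | 70/150 = 47% |
| CogState/BRIEF, 2 weeks later (10 more doses) | 38/108 = 35% | 80/150 = 53% |
| Psychologist battery, end of therapy | 108/108 = 100% | 150/150 = 100% |

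With a Day 1 baseline, 80/108 = 74% to 80/150 = 53% of scheduled ATO is still to come when CogState and BRIEF start. None is still to come when the battery starts.

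**Psychologist battery.** With a lasting deficit acquired on treatment, expected change is 0. A significant decline then appears only at the lower-tail false-positive rate, 0.01 / 2 = 0.5%. If a 6.7-point IQ deficit recovers after therapy, noncentrality is 6.7 / 20.4 × 10.95 = 3.60, and significant improvement is declared with probability 83%. Section 16.5.3 describes the two IQ subtests as used at baseline only, which does not fit a planned IQ change. The point does not depend on IQ: a 6.5-point Processing Speed recovery gives 81%.

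**CogState, assuming loss proportional to dose** (not in the documents; for illustration only)
- No prior exposure: 5 units visible, power 92%.
- 28-day Induction: 5 × (1 − 28/108) = 3.7 units visible, power 64%.
- 70-day Induction: 5 × (1 − 70/150) = 2.7 units visible, power 32%.
- For 4.3 units to be visible, the total loss must be 4.3 / (80/108) = 5.8 units, or 4.3 / (80/150) = 8.1 after a 70-day Induction.

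**What norms could show.** BRIEF scores are T-scores with mean 50 and SD 10 (Section 16.5.1). If SD is also 10 in this sample, the difference from 50 detectable with 80% power at alpha 0.017 is about (2.39 + 0.84) × 10 / √120 = 2.9 points.

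**The case against.** The strongest reply concerns CogState, the primary measure. A reader might infer that every deficit acquired on treatment is invisible. The documents do not support that. On a Day 1 baseline, 53% to 74% of scheduled ATO comes afterwards, so a Consolidation deficit that persists to 2 years off therapy falls inside the primary contrast. The Cycle 3 and end-of-therapy visits enter the mixed model and can show on-treatment change. This stands, and it limits the CogState/BRIEF point to deficits present by the first visit.

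Other tempting readings also go too far:
- **26% as a floor.** It is a share of the schedule. Section 5.1 holds ATO for differentiation syndrome, restarts it at half dose and does not make up missed doses; Sections 5.3.1 and 5.3.4 also allow holds. An individual can fall below 26%.
- **A near-total loss of power for CogState.** If 3 or 4 of the 5 units were lost before baseline, power would be 16% or 4%. Those are 60% and 80% of the loss, more than any CogState exposure share above.
- **Zero change as the wrong null because children mature.** This needs CogState to be analysed unstandardized. Calling the scores actual may only distinguish levels from changes. One unit change and one SD for all five tasks, whose scoring directions differ (Section 16.5.2), point towards a common standardized scale. The metric is not stated, so this calls for clarification only.
- **Objective 1.2.4 as unanswerable.** It is exploratory, its time points are declared openly, and late change can be estimated.

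It is also fair to say that APL is an emergency in which testing before ATO may not be feasible (the documents do not discuss this), and that norms cannot separate arsenic from acute illness, CNS bleed or socioeconomic status. Both stand. Neither gives the change score information about what happened before its baseline.

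**Conclusion.** The concern holds in limited form. For the psychologist battery it holds in full on the schedule: the baseline follows all planned ATO, so the end-of-therapy to 4-year contrast estimates late change and cannot show a lasting on-treatment deficit. For CogState and BRIEF it covers only deficits acquired by the first visit, mainly in Induction, after 26% to 47% of scheduled doses at Day 1 and somewhat more if the visit is late.

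The dose shares and the plan's power figures follow from the documents. The fall in CogState power from 92% to 64% (32% after a 70-day Induction) rests on the assumption of loss proportional to dose. The 83% figure rests on a supposed 6.7-point recovery and the plan's SD. This is a worthwhile improvement to an optional exploratory study and does not affect the primary EFS aims.

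**What to change.** In Section 9.4.4:

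1. Analyse age-standardized scores for every measure that has norms. State the CogState metric and align its scoring direction across the five tasks. At each time point, including the first, report the group mean against the normative mean with a 95% CI, alongside the change analysis. Sections 16.5.1 and 16.6 already cite BRIEF norms and a CogState standardization sample.
2. State that the battery's end-of-therapy to 4-year contrast measures late change only, and that the CogState/BRIEF contrast measures change after Induction.
3. Report how many Consolidation ATO doses preceded each first CogState/BRIEF visit, with a sensitivity analysis restricted to visits before the first such dose. This is preferable to a new visit window: Section 9.4.4 shows that the sub-study is already accruing, so a new window would mix baseline definitions. Section 16.5.2 also warns that physical complaints at testing lower scores, which argues against moving the visit closer to Induction.

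The cost is some extra analysis and a few sentences, with no new assessments or patients. Because a difference from norms cannot by itself be attributed to arsenic, it should be labelled supportive.
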